# **3.2 Baseline assessments and other participant-specific characteristics**

Demographic and participant characteristics, medical history and nicotine and alcohol use are collected pre-treatment as per SoA (CSP Section 1.3).

## **3.2.1** Demographics and participant-specific characteristics

Demographic and participant characteristics include age, age group ( $\geq 40 - < 65$ ;  $\geq 65 - 80$ , age group for EudraCT reporting purpose ( $\geq 18 - < 65$ ;  $\geq 65$ ), sex, race, ethnic group, country, height (cm), weight (kg), body mass index (kg/m^2). Age is the age at screening as reported in the eCRF. BMI (kg/m^2) is calculated as described in Section 3.8.3.

Height and weight will be allocated to the analysis visits as per Section 3.1.5. Only baseline values are included in the demographic and participant characteristics.

For subgroup analysis, participants will be allocated to geographical region depending on a country and site of the participation in this study:

• Eastern Europe: Hungary, Poland, Czech Republica;

- Western Europe and North America: Spain, Netherlands, United Kingdom, Germany, Denmark, Canada, United States;
- Rest of the world: Israel, South Africa, Australia, New Zealand, Taiwan.

(Note: new countries/regions may be introduced during the course of the study).

## 3.2.2 Medical history

Complete medical and surgical history will be collected as per SoA (CSP Section 1.3). Medical history will be coded in Medical Dictionary for Regulatory Activities (MedDRA) version 25.1 or higher.

## **3.2.3** Prior and concomitant medication

Any prior and concomitant medication(s), including herbal preparations, taken during the study will be recorded in the eCRF.

The WHO-DD March 2022 B3 Global or higher will be used to classify medications by WHO ATC classification of ingredients.

The imputation method described in Section 3.1.4 will be used in case of medication stop date partially missing. Completely missing stop date will not be imputed. Completely missing or partially missing concomitant medication start dates will not be imputed.

After the end date imputation, the medications will be classified as either prior or concomitant (but not both) according to its stop date. Prior medication is defined as any medication with a stop date prior to the first dose of IP (exclusive). Concomitant medication is defined as any medication with a stop date on or after the first dose of study drug, or any medication taken prior to study drug and that is ongoing. Medications with completely missing stop date are classified as concomitant.

Disallowed medications will include medications defined as prohibited according to CSP Section 6.5.5. They will be defined following a physician review (prior to database lock for any study delivery) of the unique combinations of ATC code classifications and generic terms captured and detailed in the Integrated Data Review Plan.

COVID-19 vaccine information will be recorded and summarised as part of concomitant medication. For reporting purposes, COVID-19 vaccines will be selected using ATC code J07BX (Other viral vaccines).

## 3.2.4 COPD history

The participant's COPD history will be collected and will include questions related to the:

- COPD first diagnosed date;
- First appearance of COPD symptoms date;
- Most recent exacerbation date;
- Number of COPD exacerbations within previous 12 months (including exacerbations resulted in antibiotic treatment, oral steroid treatment, hospitalization and total number of exacerbations);
- Number of COPD exacerbations within previous 24 months.
- Specific diagnosis of COPD (including diagnosis of chronic airway obstruction, diagnosis of emphysema, diagnosis of obstructive chronic bronchitis);
- COPD status based on GOLD Classification (including presence of chronic symptoms or respiratory failure);
- Other diagnosis of obstructive lung disease (including previous diagnosis of asthma, diagnosis of rhinitis, rhinitis seasonal or all year round).

Based on collected COPD history information, time since COPD diagnosis, time since COPD symptoms started and time since the most recent exacerbation will be calculated as described in Section 3.1.7. Partial dates will be imputes as described in Section 3.1.4.3.

COPD treatments at randomization will be collected in the eCRF as part of concomitant medication, and classified as ICS/LABA, LABA/LAMA, ICS/LABA/LAMA programmatically.

### 3.2.5 Substance usage

Alcoholic beverages status and consumption, and smoking status (cigarettes, cigars, pipes, smokeless tobacco and non-tobacco nicotine products) together with the consumption of cigarettes in pack-years will be collected.

CCI

# **3.3** Primary and secondary efficacy variables

## **3.3.1 Pre-BD clinic spirometry**

Change from baseline in pre-BD  $FEV_1$  measured in clinic at Week 12 is the primary endpoint of the study. CCI

Lung function (FEV1 and FVC) will be measured by spirometry using equipment provided by a central vendor. Spirometry testing will be performed at specified visits according to the SoA (CSP Section 1.3). CCI

## 3.3.2 Airwave Oscillometry

Change from baseline to Week 12 in AO parameters (R5-R20, R5, R20 and AX) is a secondary endpoint of this study.

AO will be performed at specified visits as detailed in the SoA (CSP Section 1.3), using the endpoints of R5-R20, R5, R20, and AX:

- Frequency dependence of Resistance, 5-20 Hz (R5-R20, measured in kPa\*s/L)
- Respiratory Resistance at 5 Hz (R5, measured in kPa\*s/L)
- Respiratory Resistance at 20 Hz (R20, measured in kPa\*s/L)
- Area under the reactance curve (AX, measured in kPa/L)

CCI

# **3.3.3 Objective cough monitoring**

Daily (ie, 24 hour) cough frequency, night-time cough frequency and awake time cough frequency are secondary endpoints for the study.

Objective cough frequency over 24 hours will be measured using an ACM (VitaloJAKTM; Vitalograph, Buckinghamshire, UK), which will be fitted and worn by the participants for approximately 24 hours after the visits detailed in the SoA (CSP Section 1.3). The device will record:

- Total counted cough events for the whole 24 hours;
- The total number of coughs flagged within 'Sleep' events;
- The total number of coughs for the full 24-hour recording minus coughs flagged within 'Sleep', 'Mute', 'Flagged Area', 'Device Not Attached' and 'Recording Ended Early' events, as calculated by the portal software.

Daily cough frequency as full average hourly cough of the full duration of recording, night time cough frequency as sleep average hourly cough of the duration of recording at night, and awake time cough frequency as awake average hourly cough of the full duration of recording minus sleep recording will be derived from the recording. All frequency data will be recorded to 2 decimal places. The minimum recording time for the measurement to be 'done' is one hour, however the minimum recording time required for analysis is 18 hours within the 24-hour interval, and participants' data with recording time < 18 hours will be excluded from analysis.

## **3.3.4 COPDCompEx events**

The COPDCompEx is a composite endpoint for exacerbations in COPD. The COPDCompEx combines exacerbations with events defined from participant e-Diaries and PEF.

Note the COPDCompEx definition typically includes dropout due to lack of efficacy as a CompEx event. However, since 'lack of efficacy' is not listed as a reason for drop out in this study, we will not include the drop out criterion for COPD CompEx in this study.

A participant will be considered to have a CompEx event during the planned Intervention Period if the participant has one or more of the following:

- COPDCompEx defined exacerbation, those collected in eCRF with at least one of the following criteria met:
  - Associated Hospitalizations = Yes;
  - Systemic Corticosteroids (injected and/or oral) = Yes;
  - Antibiotics = Yes;
  - Any emergency room visit due to COPD exacerbation? = Yes.
- A diary event An objective deterioration, which is defined as either the threshold criterion or the slope criterion (or both), being met for ≥2 consecutive days. See derivation below.

For this purpose, "2 consecutive days" means strictly the same 2 consecutive days when assessing multiple requirements within those days. For the eDiary data (which is captured twice during the day), one day will be defined by the evening/morning pairing as the other eDiary endpoints in this trial. Diary data recorded in the evening of day n and in the morning of day n+1 will belong to study day n.

#### **Derivation of Diary Events:**

The fulfilment of objective deterioration criteria will be calculated for each (single) diary variable for thresholds and slopes:

#### **Threshold criterion:**

The threshold assessment in each 2-day rolling period:

- (a)  $\geq 12\%$  decrease from baseline in morning PEF.
- (b) ≥ 1.75 doses increase from baseline in daily total rescue medication (one day is defined as evening/morning pairing. The number of doses of rescue medication is defined as the number of puffs of inhaler recorded in the evening and morning, respectively.) If either the evening or morning result is missing then the single non-missing result will be used.
- (c)  $\geq 0.75$  increase from baseline or having maximal symptom score 4 in at least one of the symptom scores: breathlessness, cough, sputum. To be specific:
  - (i)  $\geq 0.75$  increase from baseline or having maximal symptom score 4 in breathlessness daily score

or

(ii)  $\geq 0.75$  increase from baseline or having maximal symptom score 4 in cough daily score

or

(iii)  $\geq$  0.75 increase from baseline or having maximal symptom score 4 in sputum daily score.

The threshold criterion is met if [(a) or (b)] and at least one of (c) are met on 2 consecutive days.

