#### For

BCSS score,

E-RS:COPD score, Cough VAS, CCI baseline would be defined as the average from last 2 weeks (14 days) results prior to first dose of investigational product (Visit 3), ie, from evening of Study Day -14 to the morning of Study Day 1. If there are fewer than 7 completed days in the 14-day baseline period (where a complete day = entry from the evening AND the following morning, i.e. one day will include all the data performed at or after 12.00 in the afternoon up to 12.00 the following morning) then baseline will be set to missing. The baseline for the diary data used in the CompEx analysis will use the same rules. The baseline cough frequency is derived from the cough monitoring performed at Visit 2 (or Rescreening Visit 2 for rescreened participants).

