#### **Slope criterion:**

The regression slope assessment in each preceding 5-day rolling period:

- (d) Morning PEF slopes  $\leq -3\%/day$ .
- (e) Daily total rescue medication slope  $\geq 0.4$  doses/day
- (f) Slope  $\geq 0.2$ /day in all of symptom scores breathlessness, cough, sputum.

The slope criterion is met if [(d), (e) and (f)] are all met, and at least one of [(a), (b) or (c)] is met.

In all of the above cases, the regression slope is the point estimate of the slope obtained from a linear regression of the absolute values of each of the variables separately against day number, with no other variables included in the regression model.

A regression slope will be calculated provided there are at least 2 non-missing values in the required 5 days. If one or more of the variables above (d, e or f) does not have at least 2 non-missing values in the required 5 days, then the slope requirement cannot be met.

For morning PEF, the regression slope thus obtained will first also be divided by the baseline PEF value before applying the above criterion.

The following table shows how the timing for the 5-day requirement for the regression slopes fits with the 2-consecutive day requirement, where "Day 0" here refers to the first of the 2 consecutive days (shaded) to be used each time the rolling 2 consecutive day assessment is made:

	Day -4	Day -3	Day -2	Day -1	Day 0	Day 1
Threshold (a), (b), (c)					x	x
Slope	х	х	х	х	х	

 Table 21
 Timing for assessment of COPDCompEx slope criterion

A diary event can occur when (i) the threshold deterioration criterion is met for at least 2 diary variables, or when (ii) the threshold deterioration criterion is met for one diary variable, and the slope criterion is fulfilled for all included variables. In case of (i), the diary event is defined to start on the first day of the 2 consecutive deterioration days (event days 0–1). Any missing data in this 2-day window will make the event missing. In case of (ii), the event is defined to start on the first of the 2 days fulfilling the threshold criterion. This means that the slopes are calculated for days -4 to 0 of an event. At least 2 days with data are needed to calculate slopes, otherwise the event is considered missing.

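### COPDCompEx criterion (b) counts a missed diary session as zero rescue puffs, which hides real rises in reliever use, mainly when the morning entry is missed

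*SAP*

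**What the plan says.** SAP 3.3.4, Threshold criterion, sets (b) as at least 1.75 "doses increase from baseline in daily total rescue medication". A day is an evening/morning pair, and "The number of doses of rescue medication is defined as the number of puffs of inhaler recorded in the evening and morning, respectively". For incomplete pairs: "If either the evening or morning result is missing then the single non-missing result will be used".

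Criterion (b) does not act alone: "The threshold criterion is met if [(a) or (b)] and at least one of (c) are met on 2 consecutive days". Criterion (a) is morning PEF. Criterion (c) uses the breathlessness, cough and sputum scores, which are collected in the evening only (SAP 3.4.3).

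Under Slope criterion, (e) is "Daily total rescue medication slope" of at least 0.4 doses/day over five days. The combination rule is: "The slope criterion is met if [(d), (e) and (f)] are all met, and at least one of [(a), (b) or (c)] is met". The data requirement is light: "A regression slope will be calculated provided there are at least 2 non-missing values in the required 5 days".

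SAP 3.1.1 defines a complete baseline day as both sessions recorded. "If there are fewer than 7 completed days in the 14-day baseline period", baseline is set to missing, and the CompEx diary data follow the same rules. The section does not say whether incomplete days enter the baseline average.

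Two other statements bear on this. The paragraph after Table 21 in SAP 3.3.4 makes a threshold-type diary event missing if data are missing in its two-day window. SAP 3.1.4 rules out imputation for missing efficacy endpoints.

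**The concern.** A daily total is the sum of two session counts. Using one session as the total is the same as setting the other to zero. The comparison is then between a part-day count and a baseline that must contain at least seven full days. Nothing in SAP 3.3.4 scales the count, compares it with the same session at baseline, or drops the day.

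Other SAP scores treat partial data differently. E-RS:COPD and CAT totals are not calculated if an item is missing, SGRQ removes missed items from the denominator, and cough frequency is an hourly rate with an 18-hour minimum.

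Time to first COPDCompEx event is H1 in the Hochberg family (SAP 4.1.1). Protocol 4.1 relies on this endpoint for evidence on exacerbations, because it regards an FEV1 improvement as not sufficient. Entry requires only 70% diary compliance over 14 days (Protocol 5.1, criterion 11), so some missed sessions are foreseeable.

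**Working it through.** **Plan figures.** The documents give no event rate, power, reliever usage or missed-session rate for COPDCompEx. The only sample-size figure, 70 per arm for FEV1, reproduces (90 mL, SD 250 mL, one-sided 10%, 80% power) and is unaffected.

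**Threshold (b) on a part-recorded day.** Let B be baseline, T the true daily total and s the share of use in the recorded session. A full day meets (b) if T ≥ B + 1.75. Under the SAP rule a part-day meets it only if sT ≥ B + 1.75, so T ≥ (B + 1.75)/s. With s = 0.5 (assumed):

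| B | True total needed | True rise needed | Rise needed on a full day |
|---|---|---|---|
| 0 | 3.5 | 3.5 | 1.75 |
| 2 | 7.5 | 5.5 | 1.75 |
| 4 | 11.5 | 7.5 | 1.75 |
| 6 | 15.5 | 9.5 | 1.75 |

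If the recorded session carries 67% of use, B = 4 needs a rise of 4.58 (5.75/0.67 − 4). As an example, take a baseline of 4 (2+2) and a true total of 8 (4+4) with one session missed. The recorded value is 4, so the change is 0 instead of +4.

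**Which missed session matters.** A missed evening removes the symptom scores, so (c) cannot be assessed however the rescue count is handled. On a missed morning (c) survives, but morning PEF is normally missing too. Criterion (b) is then the only route through (a)-or-(b), and it is the count that is understated.

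**Size of the loss at (b).** Illustration with assumed inputs: Poisson use, known baseline of 8 puffs rising to 12 for five days, sessions missed independently, evening share 50–75%. The table gives the probability that (b) is met on two consecutive days with both evenings recorded. The lower figure in each range is for the 50% share.

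| Sessions missed | SAP rule | Proposed rule | Gain (points) |
|---|---|---|---|
| 5% | 85–86% | about 87% | 1–2 |
| 10% | 77–80% | 82–83% | 3–5 |
| 25% | 50–60% | 64–67% | 7–14 |

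These figures concern criterion (b), not whole COPDCompEx events.

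**Slope (e), if it uses the same total.** Over days −4 to 0 the least-squares slope is (−2y₁ − y₂ + y₄ + 2y₅)/10.
- Stable use of 4/day, day −4 half-recorded (2, 4, 4, 4, 4): (−4 − 4 + 4 + 8)/10 = 0.40, which meets (e) with no change in use.
- True rise 4, 4.5, 5, 5.5, 6: (−8 − 4.5 + 5.5 + 12)/10 = 0.50. With day 0 half-recorded as 3: (−8 − 4.5 + 5.5 + 6)/10 = −0.10.

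**Under the proposed rule** (missing session set to its baseline mean, even split, B = 4):
- The part-day condition becomes sT + (1 − s)B ≥ B + 1.75, so the rise needed is 1.75/s = 3.5 at any baseline.
- The true total of 8 is recorded as 4 + 2 = 6, a rise of 2, which meets (b).
- The stable series gives 4, 4, 4, 4, 4 and slope 0.
- The rising series has day 0 = 3 + 2 = 5, so (−8 − 4.5 + 5.5 + 10)/10 = 0.30. It is attenuated but no longer reversed.

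**The case against.** Several points on the other side stand.

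- **False events.** A reader might infer that the rule manufactures COPDCompEx events. The documents do not support this. Against a complete-day baseline, a part-day count cannot exceed the true total, so it cannot create a false (b). A false (e) yields an event only if the PEF slope (d), all three symptom slopes (f) and one of (a)–(c) are also met.
- **Deflated baseline.** A reader might infer that half-days pull the baseline down, so that stable users meet (b). That requires half-days to enter the average, which SAP 3.1.1 does not state. Even with the maximum of 7 half-days in 14 and an even split, the shift is a quarter of daily use, reaching 1.75 only at 7 puffs/day or more. Criterion (c) is still needed on both days.
- **Missed evenings.** No handling of the rescue count rescues the threshold rule on those days, so counting them as recoverable would overstate the gain.
- **The two-day-window sentence.** If a missed session counts as missing data, that sentence overrides the single-session rule at the threshold. The rise is then still not counted, and the distortion of (e) remains.
- **Other capture.** Deteriorations with systemic steroids, antibiotics, an emergency visit or hospitalization count from the eCRF whatever the diary shows.
- **Unknowns.** Parts of the eDiary item list in Protocol 8.1.3 are redacted, so session recall and the even split cannot be verified. A reader might suppose that entries are skipped on bad days, or more often in one arm; the documents give no evidence for either.

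**Conclusion.** The rule as written understates rescue use on any day with one missed session, and at the threshold it can hide real rises when the morning is missed. The arithmetic follows directly from the SAP; its practical size does not, because usage, split and missed-session rate are all assumed. On those assumptions the loss at (b) is small at 5–10% missed sessions and material at 25%. If the same total feeds (e), which is the natural reading but is not stated, that slope is distorted in both directions.

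The expected consequence is misclassification and reduced sensitivity in a key secondary endpoint. A biased hazard ratio is not shown: similar missingness in both blinded arms would mainly cost power, and the net effect cannot be computed from the documents. The primary analysis is untouched. The correction is inexpensive and worth making before database lock.

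**What to change.** Replace the single-session sentence in SAP 3.3.4 with: *If one session is missing, the daily total is the recorded session count plus the participant's baseline mean for the missing session. Baseline rescue use (total and per session) is calculated from complete evening-plus-morning days only.*

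Then:
- state that slope (e) uses the same derived total;
- state, in the paragraph after Table 21, whether one missed rescue session counts as missing data in the two-day window;
- note the exception to the no-imputation rule in SAP 3.1.4.

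The cost is a short SAP edit and a derivation change, with no new data. The downside is that a rise confined to the missed session is still not seen, and rises in both sessions are attenuated. Setting half-recorded days to missing would be simpler and closer to SAP 3.1.4, and would remove the slope artefact. However, it would discard part-day counts that already meet (b) on their own, so it would not recover hidden rises.

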#### 8.1.6.1 Severity of AECOPD

An AECOPD will be classified as mild, moderate, or sever based on the following criteria.

An AECOPD will be considered severe if it results in:

- An inpatient COPD-related hospitalization (Cocumentation stating that the subject was hospitalized for the COPD exacerbation or a record of the subject being admitted for  $\geq 24$  hours to an observation area, the emergency department, or other equivalent healthcare facility depending on the country and healthcare system).
- COPD-related death

An AECOPD that is not considered were will be considered moderate if it results in:

• Use of systemic corticostere its and/or antibiotics for at least 3 days; a single depot injectable dose of contractors will be considered equivalent to a 3-day course of systemic corticostere its

Exacerbations that are neither considered moderate or severe will be considered mild.

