### **B4** Calculation of BCSS scores

Table 29	BCSS © scoring

Item	Question	Score
Breathlessness	How much difficulty did you have breathing	0 – None
	today?	1 - Mild
		2 – Moderate
		3 – Marked
		4 – Severe
Cough	How was your cough today?	0 – None
		1 – Rare
		2 – Occasional
		3 – Frequent
		4 – Almost constant
Sputum	How much trouble was your sputum today?	0 – None
		1 - Mild
		2 – Moderate
		3 – Marked
		4 – Severe

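### COPDCompEx omits COPD-related death, so an untreated fatal exacerbation can be censored as event-free; the score-4 clause and two conflicting diary-event rules need smaller repairs

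*SAP*

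**What the plan says.** **Exacerbation part.** SAP 3.3.4 takes exacerbations from the eCRF and requires at least one of four things: hospitalisation, systemic corticosteroids, antibiotics or an emergency room visit. Protocol 8.1.5 lists essentially the same four routes and remarks that its definition differs somewhat from Section 8.1.6. In Protocol 8.1.6.1 an exacerbation is severe if it leads to inpatient admission or to "COPD-related death". Protocol 8.1.6.2 dates moderate and severe exacerbations from the first steroid, antibiotic or admission date.

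**Censoring.** Under SAP 3.3.4.1 a participant without an on-treatment event is censored 28 days after the last dose, or on the last eDiary day if that is earlier. Death has no rule of its own.

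**Diary part.** A diary event is "An objective deterioration, which is defined as either the threshold criterion or the slope criterion", or both, on at least two consecutive days. Threshold (a) is a morning PEF at least 12% below baseline. Threshold (b) is at least 1.75 more rescue doses per day than at baseline. Threshold (c) is a 0.75 "increase from baseline or having maximal symptom score 4 in at least one of the symptom scores: breathlessness, cough, sputum". Each symptom is a BCSS item scored 0 to 4 (for cough, "How was your cough today"; SAP Appendix B 4).

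**Combination.** Under the Threshold criterion heading: "The threshold criterion is met if [(a) or (b)] and at least one of (c) are met on 2 consecutive days". Under the Slope criterion heading the rule is stated again: "A diary event can occur when (i) the threshold deterioration criterion is met for at least 2 diary variables". The derivation opens by saying "The fulfilment of objective deterioration criteria will be calculated for each (single) diary variable for thresholds and slopes", but never says whether the three symptoms are one variable or three.

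**Role.** Time to first COPDCompEx event is hypothesis H1 in the Hochberg family of key secondary endpoints (SAP 4.1.1).

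**The concern.** Protocol 4.1 does not regard an FEV1 gain as enough by itself and looks to COPDCompEx for evidence on exacerbations. An endpoint with that job should not record a fatal exacerbation as a non-event. Censoring at or near a death from the disease under study is informative, because the participant leaves the risk set for the very reason the endpoint is meant to capture.

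The diary points concern specificity. A participant whose cough is almost constant at baseline meets (c) every day without any symptom change, so the symptom half of the test no longer tests anything for that person. If two programmers can read the combination rule differently, the event count depends on which reading is coded.

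**Working it through.** **Plan's own figure.** No event count, hazard ratio or power is given for COPDCompEx. The only sample-size figure is for FEV1: 2 × (250/90)² × (1.2816 + 0.8416)² = 69.6, so 70 per arm, as stated. It does not bear on this point.

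**Death.** Take an exacerbation that ends in death at home, with no steroid, antibiotic, admission or emergency visit, and no earlier diary event.
- Protocol 8.1.6.1: a severe exacerbation.
- SAP 3.3.4: none of the four criteria is met, so there is no COPDCompEx exacerbation.
- SAP 3.3.4.1: censored, often at the last diary day.
- Protocol 8.1.6.2: no start date can be derived, since all three dating sources are absent. Adding death therefore needs a dating rule as well.

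**Where the score-4 clause acts.** A score of 4 is already a rise of 0.75 when the baseline is at most 4 − 0.75 = 3.25. With all 14 baseline days present, the means just below and above that are 45/14 = 3.21 (rise 0.79, clause not needed) and 46/14 = 3.29 (rise 0.71, clause needed). The clause matters only from 3.29 to 4.00, where it accepts rises of 0.71 down to 0.

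**What each wording produces**, on the same two consecutive days:

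| Case | Threshold rule | Item (i), symptoms as one variable | Item (i), each symptom a variable | Threshold rule without score-4 clause |
|---|---|---|---|---|
| One symptom standing at 4; PEF and rescue unchanged | none | none | none | none |
| Two or three standing at 4; PEF and rescue unchanged | none | none | event | none |
| At least one standing at 4, plus (a) or (b) | event | event | event | none |
| (a) and (b), no symptom criterion | none | event | event | none |

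The slope route needs a slope of at least 0.2 per day "in all of symptom scores breathlessness, cough, sputum". An item fixed at 4 has slope 0, so it blocks that route.

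**How much the clause could matter.** The documents give no PEF variability, so these are assumptions: no true change, 196 days (28 weeks), first-order autocorrelated PEF, PEF-plus-symptom route only. Entries are the chance of at least one event. The first results column has 20,000 simulated participants per setting. The other two come from a separate simulation that also varies the symptom items (rounded, latent SD 0.5).

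| Day-to-day PEF SD | Symptom fixed at 4, correlation 0.2 to 0.7 | Cough at 4, correlation 0.3 to 0.5 | Mean cough about 2.2, correlation 0.3 to 0.5 |
|---|---|---|---|
| 4% | 0.2% to 4% | 1% to 4% | 0.3% to 1% |
| 6% | 22% to 58% | 35% to 48% | 12% to 21% |
| 8% | 77% to 94% | 77% to 83% | 37% to 47% |

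**Dilution of the hazard ratio**, also wholly assumed. Suppose 40% of placebo participants have an event (cumulative hazard −ln 0.6 = 0.511) and the true hazard ratio is 0.70 (active 0.358). Let a share s near ceiling have an extra event probability p in both arms, and put d = −ln(1 − sp). The ratio then reads about (0.358 + d)/(0.511 + d).
- s = 0.05, p = 0.6: d = 0.030, ratio 0.717.
- s = 0.10, p = 0.2: d = 0.020, ratio 0.71.
- s = 0.20, p = 0.6: d = 0.128, ratio 0.76.
- s = 0.20, p = 0.03 (the order seen at SD 4%): d = 0.006, ratio 0.70.

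**The case against.** **On death.** Protocol 8.1.5 openly says its definition departs from Section 8.1.6, so the omission may be deliberate. Most fatal exacerbations will also involve admission, treatment or an emergency visit. The second point stands: the gap is narrow. The first does not settle the matter, because noting a difference does not say how a COPD death is handled.

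**On the score-4 clause.** Above 3.25 a rise of 0.75 is impossible, so without the clause that item could never register worsening. This stands, and it is why the main definition should stay. Disregarding items near the ceiling in the main analysis would make the opposite error. Under the Threshold rule neither PEF nor rescue use makes an event without (c), so a participant with all three items at ceiling would lose the threshold route and, in effect, the slope route too. In the simulation at SD 6%, ignoring items with a baseline of 3.5 or more gave ceiling participants a 7% to 13% chance of an event, below the 12% to 21% of ordinary participants.

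**Stronger readings a reader might infer.**
- That unchanged participants gain events. Under the Threshold rule they do not, because PEF or rescue use must also cross its limit on the same two days. It would be true only under item (i) with each symptom counted separately and at least two standing at 4.
- That the entry rule concentrates ceiling scorers. It asks for a mean of at least 2 in cough and in sputum, which says nothing about means above 3.25. No baseline distribution is given.
- That the clause favours one arm. The rule is the same in both. Spurious events dilute; a drug that moved cough from 4 to 3 would remove some. No net direction follows from the documents.

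**Conclusion.** The omission of death holds on the text of both documents, with no assumption needed. Its numerical effect is likely to be very small: it needs a fatal exacerbation inside the on-treatment window with none of the four criteria and no earlier diary event. The documents give no death rate from which to count such cases. It deserves repair because the repair is cheap and the censoring is informative.

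The score-4 point holds in a limited form: for items with a baseline above 3.25, a diary event can rest on PEF or rescue fluctuation alone. Its size cannot be determined from the documents, since PEF noise, the share near ceiling, the event rate and the hazard ratio are all assumed above. It is negligible at an SD of 4%, and even at the unfavourable corner shown a hazard ratio of 0.70 moves only to about 0.76.

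The conflict between the two combination rules is plain from the text. They disagree on (a) with (b) but without (c) and, if symptoms count separately, on two symptoms standing at 4. The primary endpoint and the sample size are unaffected.

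**What to change.** 1. **Death.** In SAP 3.3.4 add COPD-related death within the on-treatment window as a qualifying COPDCompEx event. Date it at the recorded exacerbation onset or, if there is none, at the date of death. Protocol 8.3.2 already collects the date and probable cause of death, so no new data are needed. List it in SAP Section 6 as a change from Protocol 8.1.5. Cost: one line for the criterion, one for the date and one in Section 6.
2. **Score-4 clause.** Keep it in the main definition. Add one sensitivity analysis of time to first COPDCompEx event in which a score of 4 does not count for an item whose baseline is at or near 4. Fix the cut-off before unblinding; a cut-off at 3.25 is the same as deleting the clause. Cost: one further Cox run. Participants at ceiling are under-counted in that run, which is why it should not be the main analysis.
3. **Combination rule.** Reconcile the Threshold criterion with item (i) under the Slope criterion. State whether the three symptoms form one variable or three, and whether (a) with (b) but without (c) is an event. If the Threshold rule is the intended one, item (i) need only refer back to it. Cost: one or two sentences.
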